5.7 Participant Withdrawal or Termination

5.7.1 Reasons for Withdrawal or Termination

Participants are free to withdraw from participation in the study at any time upon request. An investigator may terminate participation in the study if:

- Any clinical adverse event (AE), laboratory abnormality, or other medical condition or situation occurs such that continued participation in the study would not be in the best interest of the participant
- The participant meets an exclusion criterion (either newly developed or not previously recognized) that precludes further study participation.

5.7.2 Handling of Participant Withdrawals or Termination

If a participant wishes to withdraw from the study they may do so at any point without adverse effect on their standard-of-care treatment. Participants will be provided with study team e-mail and contact number and can withdraw at any time

5.8 Premature Termination or Suspension of Study

This study may be temporarily suspended or prematurely terminated if there is sufficient reasonable cause. If the study is prematurely terminated or suspended, the PI will promptly inform the IRB and will provide the reason(s) for the termination or suspension.

Circumstances that may warrant termination or suspension include, but are not limited to:

- Determination of unexpected, significant, or unacceptable risk to participants
- Demonstration of efficacy that would warrant stopping
- Insufficient compliance to protocol requirements
- Data that are not sufficiently complete and/or evaluable
- Determination of futility

Study may resume once concerns about safety, protocol compliance, data quality are addressed and satisfy the sponsor, IRB and/or FDA.

6 Study Device Intervention

6.1 Study Device Description

tDCS is a device that delivers weak electrical current (2.0 mA) through sponge electrodes placed on the scalp. The main components are:

- **1x1 Mini CT tDCS device:** The device is powered by 9-volt (V) rechargeable batteries. The device can be easily operated, with a user-friendly large-button keypad interface. The device allows strict dose control and usage control, employing a one-time use code provided by the study technician to unlock the device for each stimulation session. The high sensitivity of the device to any changes allows us to monitor in real time the contact quality between the surface of the electrode and the skin ensuring safety and high quality of the delivered stimulation.
- **tDCS Headset:** The headset will be used to standardize and simplify the electrode placement. The headset uses two electrodes: the anode electrode and the cathode electrode. The DLPFC (anode over F3 and cathode over F4) electrode montage will be used to target the left prefrontal cortex. The headset connects to the tDCS device with two wires (anode and cathode).
- **Sponge electrodes:** The electrodes are square (5 x 5 cm²) pre-saturated saline sponge electrodes packaged for single use equipped with snaps to fasten the sponges to the headset. The participant will be only required to open the package and snap the sponge onto the headset. The use of pre-moistened,

CONFIDENTIAL

This material is the property of the NYU School of Medicine and Langone Medical Center. Do not disclose or use except as authorized in writing by the study sponsor
Interventional Template Version: 11 January 2019

single-use electrodes avoids the possibility of over-saturating the sponge as this can saturate the hair, affecting the spread and the direction of the current flow.

tDCS is a non-significant risk device because it is:

1. not intended as an implant,
2. it is not purported or represented to be for use supporting or sustaining human life,
3. it is not for a use of substantial importance in diagnosing, curing, mitigating, or treating disease or otherwise prevent impairment of human health and does not present a potential for serious risk to the health, safety, or welfare of a subject. tDCS has an established record of safety and tolerability for use from trials in a range of neurological and psychiatric conditions^{106 107}, and including the specific remotely supervised and at-home use as proposed for this study^{108 109}. It has NSR designation for our trials specifically using the proposed procedures in participants with MS^{110 111}
^{112 113 114 115 116} as well as for use as an NYU Langone Health approval as innovative care for our tDCS clinical service program¹¹⁷.
4. it does not otherwise present a potential for serious risk to the health, safety, or welfare of a subject.

Attached is an NSR determination letter for FDA review of its use in a vulnerable population (developmentally disabled children).

6.1.1 Acquisition

The device will be provided by Soterix Medical Inc.

6.1.2 Product Storage and Stability

Devices, when not allocated to participants, are stored in-house in a locked room. Device allocation notes including device serial number and device unlock codes will be stored for reference.

6.1.3 Device Programming

To ensure blinding, devices will be pre-programmed in advance by an independent staff member, who will not take part in the treatment and assessment¹¹⁸⁻¹²⁰.

For active tDCS, the device is programmed to ramp up to 2.0 mA (for 30 seconds), provide constant current throughout session (19 minutes), and then ramp down (for 30 seconds) at the end.

For sham tDCS, the device is programmed to ramp up to 2.0 mA (for 30 seconds) followed by a ramp down (30 seconds), with no current delivery for 18 minutes, and then ramp up (for 30 seconds) and down (for 30 seconds) at the end.

6.1.4 Dosing and Administration

The tDCS device will deliver each session 2.0 mA for 20 minutes over the DLPFC. Participants will receive 20 intervention sessions over the course of this study on weekdays (M-F).

Study technicians are always live with participants via Zoom or Webex when initiating and delivering the treatment and can address any issues that arise during treatment. Study technicians will direct headset placement remotely. The tDCS device can only operate if: **1)** the headset is correctly placed for adequate connection, and **2)** the study technician provides a session code that unlocks the device for a one-time only 20-minute period of use.

If the device loses adequate electrode contact for any reason, the device will automatically discontinue the session. The session can only be reestablished if another unlock code is provided by the study technician. Specific stop criteria are outlined for treatment administration. Should any stop criteria be met at any point in administration of treatment, the participant will not undergo any further treatments and will be asked to return the study equipment (See Fig 3). If the participant wishes to discontinue a session, they may press the "abort" key at any time, which ramps down and stops the stimulation current within 30 seconds.

CONFIDENTIAL

This material is the property of the NYU School of Medicine and Langone Medical Center. Do not disclose or use except as authorized in writing by the study sponsor
Interventional Template Version: 11 January 2019

6.1.5 Route of Administration

tDCS is administered through a paired of sponge electrodes placed on the scalp using the headset. The device allows strict usage control, employing a one-time use code provided by the study technician to unlock the device for each stimulation session.

6.1.6 Duration of Intervention

Participants will complete 20 sessions of either active or sham RS-tDCS over the course of approximately 4-6 weeks. The tDCS will be programmed to deliver 20 minutes of stimulation.

6.1.7 Device Specific Considerations

- Device size: Height 7.2 in; Width 3.6 in; Depth 1.2 in
- Device model: Model 1601
- Device settings and programming: Double-blind option: Sham (ON/OFF), Secure administrator mode to program sessions, storage of data and codes of 250 sessions; SMARTscan to provide continuous visual indication of electrode quality during stimulation

6.2 Study Device Accountability Procedures

The device accountability and inventory log will be used to log device-use including subject ID, date shipped, dates used, session technician, and date returned.

7 Study Behavioral Intervention

7.1.1 Mindfulness meditation

The “10-Minute Mind” consists of guided mindfulness mediation audio tracks based on the “10 Minute Mind” program developed by Monique Rhodes. These guided meditations are built on the growing body of research for efficacy of mindfulness meditation for reducing psychological distress, including in CUD. Importantly, these audio tracks will be tailored specifically for use in this trial, to address both distress and cannabis use and timed to be paired to the 20 minutes period of tDCS. The 10 Minute Mind tracks will be downloaded on the laptop computer loaned to the study participants of both active and sham Arms.

7.1.2 Administration of Intervention

Participants will receive an laptop computer with the downloaded meditation audio tracks.

8 Study Procedures and Schedule

8.1 Study Procedures

After subjects provide written informed consent, the following research procedures will take place over approximately 4 months:

- A study clinician will conduct a telehealth research screening through Zoom, Webex or phone call to review patients' medical history and confirm eligibility criteria. Ineligible patients may be referred for standard-of-care by the study clinician.
- If eligible, a study team member who is not involved in treatment delivery or assessment will randomize a device. The study equipment, including the tDCS device, headset, saline sponges, single panel cannabis test kit, and laptop computer will be shipped to the participant. The laptop computer will be pre-programmed with the meditation mindfulness programs.
- Baseline & tDCS Session 1:

CONFIDENTIAL

This material is the property of the NYU School of Medicine and Langone Medical Center. Do not disclose or use except as authorized in writing by the study sponsor
Interventional Template Version: 11 January 2019

- Following procedures for our validated protocol^{85-89,91-95}, participants will first receive training on the use of the tDCS device and headset.
- Participants will undergo a 90-second tDCS tolerability test to ensure the stimulation is tolerable. The participant will be given a one-time use code to initiate the stimulation, the tDCS device will ramp up to its target stimulation intensity (2.0mA) and after 90 seconds, participants will be instructed to press “0” to stop the test. Participants are free to stop the test at any time before the 90 seconds. Participants will then be instructed to remove the headset. Participants who cannot tolerate 2.0 mA will be considered a screen failure.
- Participants will be asked to complete a single panel cannabis test by following the instructions included in the test kit. This remote video method of urine strip testing has been used in other studies of participants with substance use disorders in rural communities¹²¹. Following these established protocols, the participant will be instructed to collect a urine sample in the collection cup (off camera) and then in view of the study technician will place a test strip into the cup and show the results. Participants will then be told to follow the disposal procedures included in the kit and wash their hands.

While the remote connection does allow for a participant to provide a sample that is not their own to test, we believe that this occurrence would be of very low likelihood in this study sample. The participants are enrolled based on disclosed cannabis use, they are not incentivized in any way to decrease their cannabis use, and there would be no other primary or secondary gain for invalidating this procedure. Alternatively, in the similarly unlikely event that participants have falsely reported cannabis use and test negative at baseline, they will be withdrawn.

- Participants will complete self-report questionnaires about their physical and mental health, and cannabis use through REDCap survey function (see assessments section 8.2 below).
- For exploratory research, participants will complete cognitive measures (BICAMS, Cogstate Brief Battery) and MS symptom questionnaires.
- Participants will have their first 20-minute tDCS session of either 2.0mA active or sham tDCS combined with mindfulness meditation. At each treatment session, participants will complete brief adverse event reports before and after each session. Once the study technician visually confirms correct headset placement and participants confirms adequate contact quality (moderate or good), the technician will provide the participant with a one-time use unlock code to enter into their tDCS device. The participant enters the code when ready to initiate the stimulation. During each stimulation session participants will listen to a guided mindfulness meditation audio track on the study provided laptop computer.
- Remotely-Supervised tDCS Sessions 2-20:
 - Over the next 4-6 weeks, participants will complete the remaining daily tDCS + mindfulness meditations as described above for session 1.
 - After sessions 5, 10, and 15 participants will complete self-report questionnaires using REDCap survey function.
 - tDCS session 20 & Treatment-end: After completing the final tDCS session participants will repeat the baseline self-report questionnaires and measures, and the single panel cannabis test. Participants will be asked to return the equipment via Fedex using a prepaid return label.
- Post treatment-end follow-ups

CONFIDENTIAL

Participants will have 3 follow-ups at 1, 2 and 3 months post treatment-end to repeat the questionnaires. At the 3-month follow-up the participant's will also be given a single panel cannabis test and asked a brief blinding integrity questionnaire (i.e. which group they think they were in) and then unblinded.

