2.4 Potential Risks & Benefits

2.4.1 Known Potential Risks

- Risks of tDCS:** The repeated application of tDCS as proposed in this study poses a non-significant risk (NSR) to participants. The safety of this technique has been addressed and tested by multiple researchers who have concluded that tDCS, as applied in a manner similar to our proposed protocol, induces only mild and transient side effects with no report of serious adverse event related to tDCS across clinical trials to date. In >9,000 participant, no undesirable or long-lasting effects have been reported, nor have any subjects reportedly abandoned a study due to discomfort. The most common side effects are warming sensation, itching or tingling sensation under the area of the electrodes. The tDCS protocol of this proposed research will use a stimulation intensity of 2.0 mA that falls well within safety limits established by numerous previous studies applying tDCS with human subjects. In both active and sham tDCS treatment arms, there could be mild discomfort from wearing the headgear.

The protocol is designed to have a decision-tree series of checkpoints with "STOP" criteria that must be cleared in order to proceed at each step (see Fig.3).

Figure 3. Safety and Tolerability checkpoints and stop criteria

CONFIDENTIAL

This material is the property of the NYU School of Medicine and Langone Medical Center. Do not disclose or use except as authorized in writing by the study sponsor
Interventional Template Version: 11 January 2019

- **Guided mindfulness meditation:** Mindfulness meditation is not associated with any known risk. To minimize possible frustrating feeling, each session will be monitored in real-time via HIPAA-compliant videoconference with a trained study technician.
- **Self-report questionnaires:** Completing questionnaires about one's physical and mental health and cannabis use may produce some discomfort and/or emotional distress in some patients. Participants will be allowed to take breaks as needed and may skip questions they do not feel comfortable answering so long as the questions do not affect analysis of primary endpoints or eligibility criteria. While we don't anticipate this population to have suicidal ideation, [name] MD will screen for suicidality as part of the research eligibility screening and will follow standard clinical procedures if a subject is suicidal (e.g. refer subject to closest emergency room).

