8.3.2 Electronic Consent & Telehealth medical screening (Visit 1)

- Remote e-consent through SendSafe (*20 minutes*)
- Telehealth medical screen with the study clinician to review medical history and medication history [non-NYU patients may be asked to provide their medical records (e.g. fax to NYU study location)], and determine eligibility based on inclusion/exclusion criteria. (*1 hour*)
- Eligible participants will be scheduled for a baseline visit. A team member who is not involved in the administration of study procedures will randomize and program a tDCS device and study equipment will be shipped to participant.

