10.4.3 Safety Analyses

The tolerability of the RS-tDCS system will be assessed by both the Adverse Event Report frequency (which will be compared with Fisher's exact test with active and sham as categories, and the mean cumulative function (MCF) for analyzing multiple/repeated occurring AEs to subjects during the treatment period), and participant retention in the study.

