10.5 Sample Size

Power analyses were conducted independently for Aim 1 and Aim 2, wherein estimated effect sizes came from 2 independent manuscripts that used tDCS to measure changes in distress (Aim1) and estimated changes in cannabis use (Aim 2). In the planned study subjects will be assessed at 5 time points with the Change from V1 being used as a dependent variable (4 pieces of data per dependent measure per participant).

There is an anticipated interclass correlation coefficient (ICC) of 0.8 for the within-subjects measures. The design effect which accounts for multiple correlated observations within each subject, is estimated to be 4.2 ($DE = [1 + (5-1) 0.8]$). In a clustered setting, the sample size is $N_{\text{effective}} = nm/DE$ where n is the number of subjects required when m replications within participants are performed after accounting for the design effect (DE). The estimated number of individuals needed to detect an effect in the active RS-tDCS group is 28 for Aim 1 and 15 for Aim 2 (1-sided alpha of 0.05 and power of 80%).

CONFIDENTIAL

This material is the property of the NYU School of Medicine and Langone Medical Center. Do not disclose or use except as authorized in writing by the study sponsor
Interventional Template Version: 11 January 2019

For this study, we will utilize a 2:1 randomization based on pragmatic considerations including timeline, cost, and the added value of over recruiting to the Active group in order to have a better assessment of safety and tolerability data. In corporation this information into the total planned recruitment size, we arrived at n=42(=50 * 4.2 / 5). (28 allocated to active, 14 allocated to sham). We anticipate enrolling 52 participants which includes 10% drop out rate.

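### Failing the 90-second 2.0 mA test is labelled a screen failure although it happens after randomization, and no tolerability measure in section 10.4.3 counts it

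*Combined protocol and SAP*

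**What the plan says.** Under section 8.1 eligibility is confirmed at the telehealth screening, after which "a study team member who is not involved in treatment delivery or assessment will randomize a device" and the equipment is shipped. Section 8.3.2 gives the same order: a team member "will randomize and program a tDCS device and study equipment will be shipped to participant". At the next visit (Visit 2, sections 8.1 and 8.3.3), "Participants will undergo a 90-second tDCS tolerability test to ensure the stimulation is tolerable". The rule for anyone who does not pass is "Participants who cannot tolerate 2.0 mA will be considered a screen failure".

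Section 10.3 states that all analyses are run on two samples: all randomized subjects (n=52), and those who completed all 20 sessions.

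Section 10.4.3 defines the tolerability analysis: "The tolerability of the RS-tDCS system will be assessed by both the Adverse Event Report frequency", compared between arms with Fisher's exact test, together with a mean cumulative function for "analyzing multiple/repeated occurring AEs to subjects during the treatment period), and participant retention in the study". Section 10.5 gives as one reason for 2:1 allocation the value of "over recruiting to the Active group in order to have a better assessment of safety and tolerability data".

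**The concern.** A screen failure is normally someone found ineligible before allocation. Here the person has consented, been judged eligible and had a device randomized and programmed. Tolerance of 2.0 mA is not among the inclusion or exclusion criteria in 5.1 and 5.2. At the same visit, a participant who tests negative for cannabis is to be withdrawn (8.1), so two exits at one visit carry different labels.

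The label matters because of what 10.4.3 counts. The brief adverse event reports are tied to treatment sessions (8.1), the mean cumulative function covers the treatment period, and a screen failure would ordinarily not be a retention loss. Someone who could not complete the test therefore has no named place in the tolerability results. Followed as written, the rule takes people who did not tolerate the current out of the retention figure, in a trial that gives better tolerability data as a reason for its allocation ratio.

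**Working it through.** **Order of events**

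| Step | Source |
|---|---|
| Consent, then screening confirms eligibility (Visit 1) | 8.1, 8.3.2 |
| Device randomized, programmed, shipped | 8.1, 8.3.2 |
| 90-second test at 2.0 mA (Visit 2) | 8.1, 8.3.3 |
| Cannot tolerate: screen failure | 8.1 |
| Session 1, with brief adverse event reports before and after | 8.1 |

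The exit lies between randomization and the first treatment session.

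**Where a failed test could be counted**

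- Adverse event frequency: 9.3 records events from consent onward, so a symptom may be captured. The number of people unable to complete the test is not. In the schedule of events the adverse event row appears to start at sessions 1-4, but that table is flattened in the available text and should be read with caution.
- Mean cumulative function: restricted to the treatment period.
- Retention: no denominator is given. Under 10.3 it is everyone randomized; under the 8.1 label it would ordinarily leave these people out. The second sample in 10.3 consists of completers, so it cannot show loss.
- Monitoring: 9.7.1 reviews screen failures under enrolment, with no requirement for reason or arm.

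**Size**

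The documents give no first-exposure intolerance rate and no tolerability figure to reproduce. The rates below are assumptions. The number tested is set at 52, the all-randomized figure in 10.3. It would be lower if some of those who consent fail screening at Visit 1.

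Expected failures = 52p; P(at least one) = 1 − (1 − p)^52.

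| Assumed p | Expected failures | P(at least one) |
|---|---|---|
| 0.5% | 0.26 | 0.23 |
| 1% | 0.52 | 0.41 |
| 2% | 1.04 | 0.65 |
| 5% | 2.6 | 0.93 |
| 10% | 5.2 | 0.996 |

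The next table shows the effect of the label alone, with no later intolerance and no other loss. Intervals are exact (Clopper-Pearson) 95%.

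| Failures | Intolerance, failures excluded | Intolerance, all randomized | Retention, excluded | Retention, all randomized |
|---|---|---|---|---|
| 0 | 0/52 (0 to 6.8%) | 0/52 (0 to 6.8%) | 52/52 | 52/52 |
| 3 | 0/49 (0 to 7.3%) | 3/52 = 5.8% (1.2% to 15.9%) | 49/49 = 100% | 49/52 = 94.2% |
| 5 | 0/47 (0 to 7.5%) | 5/52 = 9.6% (3.2% to 21.0%) | 47/47 = 100% | 47/52 = 90.4% |

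**What the test delivers in each arm**

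Section 8.1 describes one procedure, ramping to 2.0 mA and stopping at 90 seconds. Section 6.1.3 gives the session programs. If those also govern the test, an active device ramps for 30 seconds and holds 2.0 mA for the remaining 90 − 30 = 60. A sham device ramps up for 30, down for 30, and is off for the last 90 − 60 = 30. The documents do not say whether they do.

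At 2:1, 52 people split about 35 and 17 (52 × 2/3 = 34.7). Fisher's exact test on 5 against 0 failures gives p = 0.16, and on 3 against 0 gives p = 0.54, so a by-arm count would be descriptive.

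**The case against.** The strongest reply is that the documents already cover these people. Section 10.3 puts all randomized subjects in all analyses, 9.3 requires adverse events to be recorded from consent with an inquiry at every visit, and 9.7.1 has screen failures reviewed at documented meetings with an annual report to the IRB. This defeats three stronger readings that a reader might infer.

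- That intolerance at first exposure goes unreported. It may appear as an adverse event or in a monitoring report; what is missing is a planned place in the tolerability results.
- That the tolerability analysis is confined to people who passed the test. Section 10.4.3 sets no denominator, and 10.3 points the other way. The text is contradictory, not settled. Nor does passing for 90 seconds show tolerance of 20 sessions of 20 minutes: later intolerance can still surface through session reports, aborted sessions, the stop criteria and retention.
- That the active-sham comparison is biased. If the test is identical in both arms, the exclusion narrows whom the result describes without favouring an arm. Whether it is identical is not stated.

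A reader might also suppose that the tolerability figure feeds the follow-on grant. Section 10.4.2 ties that grant to efficacy effect sizes, so the documents do not support this.

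The background also suggests that failures may be rare: 2.2.2 reports completion above 97%, and 2.4.1 says of prior studies "nor have any subjects reportedly abandoned a study due to discomfort". That is why the range above starts at 0.5%. Figure 3, on checkpoints and stop criteria, is not shown in the available text and may address this step.

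What the reply does not remove is the conflict between 8.1 and 10.3. Applying 10.3 alone would not repair the adverse event measure either: with no report tied to the test, a person who failed it could enter Fisher's test as free of events.

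**Conclusion.** The point holds as a post-randomization exclusion that contradicts the all-randomized analysis set, combined with a tolerability plan that has no line for the event. Its size depends on an intolerance rate that the documents do not give. At the low end of the assumed range (0.5%) there would most likely be no failures, and the two ways of counting would agree. At 5% to 10%, at least one failure is very likely, and retention could be overstated by up to about 10 percentage points (five failures: 100% against 90.4%). These figures assume that all 52 are randomized and tested, and that the screen-failure label is followed when retention is computed. The primary efficacy conclusions are not shown to be wrong. The gap should be closed before analysis because the correction is small and the direction of the error is known: it favours the device.

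**What to change.** Reconcile 8.1, 10.3 and 10.4.3 as follows.

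- **8.1:** record the outcome as discontinuation for intolerance after randomization instead of screen failure.
- **10.3:** state that these people stay in the all-randomized set and count as discontinuations in the retention summary.
- **10.4.3:** report the number and proportion of participants who start the tolerability test and cannot complete it, by allocated arm, with reasons and an exact 95% confidence interval, beside the session adverse event summaries.
- **6.1.3 or 8.1:** state whether sham-programmed devices deliver the same 90-second exposure during the test, because the by-arm count cannot be interpreted without it.

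This changes classification and reporting only; who may continue treatment is untouched. The cost is a few sentences and one table row. The technician already supervises the test live, so no new procedure is needed. The downside is a tolerability and retention figure that may look slightly less favourable.
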